By my signature, I agree to personally supervise the conduct of this study and to ensure its conduct in compliance with the protocol, informed consent, IRB/HRPO procedures, the Declaration of Helsinki, ICH Good Clinical Practices guidelines, and the applicable parts of the United States Code of Federal Regulations or local regulations governing the conduct of clinical studies.

Primary Objective

To determine the clinical response rate of patients with Stage I-III B (cT1-3, N0-1, M0) rectal cancer being treated with sequential short course radiotherapy followed by 8 cycles of multi-drug chemotherapy.

Secondary Objectives:

1. To obtain prospective patient reported outcomes from an organ preservation approach towards early stage rectal cancer
2. To determine the incidence of any grade ≥ 3 toxicity during treatment
3. To determine the incidence of post chemoradiotherapy grade ≥ 3 toxicity at 1 year
4. Determine quality of anorectal function at 1 year using the FACT-C questionnaire

Table of Contents

SCHEMA.....	5
1 BACKGROUND.....	8
2 OBJECTIVES.....	9
2.1 Primary Objective	9
2.2 Secondary Objectives.....	9
3 ELIGIBILITY CRITERIA	10
3.1 Inclusion Criteria.....	10
3.2 Exclusion Criteria.....	10
3.3 Inclusion of Women and Minorities.....	11
4 Patient Registration.....	11
4.1 Confirmation of Patient Eligibility.....	11
4.2 Patient Registration in the Siteman Cancer Center OnCore Database.....	11
4.3 Assignment of UPN	12
5 EVALUATION STUDIES.....	12
5.1 Pre-treatment	12
5.2 During Radiotherapy and Chemotherapy.....	12
5.3 Completion of Chemotherapy/Post-Treatment Evaluation	13
5.4 Follow-up	13
6 RADIATION THERAPY GUIDELINES.....	13
6.1 Dose, Fractionation	13
6.2 Treatment Planning Procedures	14
6.3 Simulation Procedures/Patient Positioning	14
6.4 Clinical Target Volume (CTV) and Planning Target Volume (PTV) Definitions.....	14
6.5 Normal Tissue Contours.....	15
7 CHEMOTHERAPY GUIDELINES.....	15
7.1 Chemotherapy Schedule and Doses	15
7.2 Agent Administration.....	15
7.3 Supportive Care Recommendations	16
8 DOSE DELAYS/DOSE MODIFICATIONS.....	16
8.1 Dose Levels.....	17
8.2 Dose Modifications for Toxicity Related to FOLFOX-6.....	18
8.3 Dose Modifications for Neurologic Toxicity (Paresthesia or Dysesthesia) Related to Oxaliplatin.....	19
9 ADVERSE EVENT REPORTING	19
9.1 Definitions.....	19
9.2 Reporting to the Human Research Protection Office (HRPO) at Washington University 21	

1 BACKGROUND

With the exception of a small group of favorable risk stage I disease, the standard of care for stage I-III rectal cancer usually includes a total mesorectal excision (TME). TME in the form of an abdominoperineal resection (APR) results in a permanent stoma, which may significantly impact the patient's self-image and quality of life (QOL). TME in the form of a low anterior resection (LAR) obviates the need of an ostomy but is associated with poorer rectal function.

There are increasing data supporting the use of chemotherapy and radiation therapy for non-operative management of rectal cancer¹⁻⁴. Habr-Gama et al. treated 70 distal rectal cancer (T2-4 N0-2) patients with 54 Gy in 30 fractions and concurrent 5-fluorouracil (5FU)/leucovorin and demonstrated an initial complete clinical response (cCR) in 47 (68%) patients with 39 (57%) demonstrating a sustained cCR at 56 months⁴. Appelt et al. treated 55 patients (T2-3 N0-1) with 60 Gy in 30 fractions with a 5 Gy brachytherapy boost plus oral tegafur-uracil⁵. Seventy-eight percent of patients demonstrated cCR with 16% local recurrence at 24 months⁵. Maas et al. found that patients with cCR after neoadjuvant chemoradiation therapy have similar oncologic outcomes to those with pathologic complete response (pCR)⁶. The radiation in these trials was delivered over 5-6 weeks of daily treatment.

Short course radiation therapy delivered as 25 Gy in 5 fractions is routinely used as preoperative therapy in Europe and Australia⁷⁻⁹. The first Polish rectal study demonstrated that patients with T3-4 resectable rectal cancer treated with 25 Gy in 5 fractions followed by surgery versus 50.4 Gy in 28 fractions with concurrent 5FU followed by surgery had similar local recurrence (9% vs 14%), disease free survival (58% vs 56%) and overall survival (67% vs 66%)⁸. The second Polish rectal trial demonstrated that there was no difference in R0 resection and pCR rates in patients with T3-4 rectal cancer treated with 25 Gy in 5 fractions followed by FOLFOX then surgery compared to 50.4 in 28 fractions with FOLFOX followed by surgery⁹. There was even a 3 year overall survival advantage for short course radiation (73% versus 65%), but the reason for this survival advantage in light of a non-significant difference in disease free survival is unclear. Important to note is that the dose prescribed with pre-operative short course radiation (5 Gy x 5 fractions) has a biologic effective dose (BED) of 37.5 Gy ($\alpha/\beta=10$) in contrast to the BED of 63.7 Gy when 54 Gy is given in 30 daily fractions. Increasing the radiation dose to the tumor may further increase the clinical complete response (cCR) rate and allow for non-operative management.

There are increasing data to support increasing the interval from radiation to surgery. The pCR rate of standard short course radiation followed by surgery 1 week later is approximately 1%^{7,8}. Increasing the interval to surgery from 2 to 6-8 weeks may increase the pCR rate without compromising oncologic outcomes¹⁰⁻¹². The Lyon R90-01 trial demonstrated that patients with T2 rectal adenocarcinoma treated with 39 Gy in 13 fractions had increased pCR if surgery is delayed to 6-8 weeks post-radiation versus 2 weeks post-radiation (26% vs 10%)¹⁰. In the non-inferiority Stockholm III, which evaluated short course radiation followed by surgery at 1 versus 4-8 weeks versus long course radiation therapy, there were no differences in long term cancer outcomes between the three treatment groups¹³. Thus increasing the interval from radiation completion to surgery may improve treatment outcomes.

In a phase II trial for patients with cT3-4, any N, any M rectal cancer recently completed at Washington University (HRPO# 09-0696) evaluating short-course radiotherapy followed by 4 cycles of FOLFOX chemotherapy (5FU, oxaliplatin, and leucovorin), a complete tumor response was seen in 28% of patients, with a complete pathologic response rate of 42% and downstaging rate of 87% for patients with lower risk tumors (3). QOL data was prospectively evaluated using the Functional Assessment of Cancer Therapy-Colorectal (FACT-C) questionnaire. Mean FACT-C scores for all five categories were not significantly different for pre-treatment (20.6 +/- 5.6), pre-surgery (20.2 +/- 5.4), or post-surgery time points (20.0 +/- 5.4) (p = 0.8), confirming clinically observed absence of treatment related toxicity. Improved patient-reported functional outcomes were observed for patients undergoing sphincter sparing surgery, compared to those requiring an abdominoperineal resection with ostomy. In patients with an ostomy, FACT-C scores for functional well-being 1-year post-surgery were significantly reduced (lower QOL) compared to patients without ostomy (13.2 vs 19.2, p = 0.01) (2). Given the negative quality of life impact of abdominoperineal resection with ostomy, it is plausible that the side effect profile of radiation therapy and chemotherapy may allow improved overall quality of life in the context of an organ preservation strategy.

To date, short course radiation therapy has not been evaluated in the setting of non-operative management. Given the highly favorable response rates reported in higher risk stage II-III patients and patient-reported outcomes data which confirm a benefit to sphincter sparing approaches, we propose a pilot study of organ preservation treatment for rectal cancer which would otherwise require total mesorectal excision (TME).

2 OBJECTIVES

Our principal objectives in this trial will be to determine if short course radiotherapy followed by 8 cycles of chemotherapy results in cCR, to permit an organ preservation strategy for patients with stage I-IIIB (cT1-3, N0-2, M0) rectal cancer. We do not anticipate being able to prove this in the present single arm pilot study; that would be the principal objective of a successor, multi-institution phase II/III protocol.

2.1 Primary Objective

To determine the cCR response rate of patients with stage I-IIIB (cT1-3, N0-2, M0) rectal cancer being treated with sequential short course radiotherapy followed by 8 cycles of multi-drug chemotherapy.

2.2 Secondary Objectives

1. To obtain prospective patient reported outcomes from an organ preservation approach for early stage rectal cancer.
2. To determine the incidence of any grade ≥ 3 toxicity during treatment.
3. To determine the incidence of post chemoradiotherapy grade ≥ 3 toxicity at 1 year
4. To determine quality of anorectal function at 1 year using the FACT-C questionnaire.

3 ELIGIBILITY CRITERIA

3.1 Inclusion Criteria

1. Diagnosis of biopsy proven stage I-III B (cT1-3, N0-2, M0) adenocarcinoma of the rectum; staging must also be based on multidisciplinary evaluation including MRI and/or endorectal ultrasound
2. Tumor \leq 12 cm from anal verge as determined by MRI or endoscopy
3. ECOG performance status 0-2
4. At least 18 years of age
5. Adequate bone marrow function defined as:
 - a. ANC $>$ 1,500 cells/mm³
 - b. Hgb $>$ 8 g/dl
 - c. platelets $>$ 100,000 cells/mm³
6. Women of childbearing potential and men must agree to use adequate contraception (hormonal or barrier method of birth control, abstinence) prior to study entry and for the duration of study participation. Should a woman become pregnant or suspect she is pregnant while participating in this study, she must inform her treating physician immediately.
7. Able to understand and willing to sign an IRB-approved written informed consent document.

3.2 Exclusion Criteria

1. No clinically detectable (MR, endoscopy or DRE) tumor present.
2. Prior radiation therapy, chemotherapy or extirpative surgery for rectal cancer.
3. Any evidence of disease from another malignancy or history of other malignancy \leq 3 years previous (with the exception of basal cell or squamous cell carcinoma of the skin which were treated with local resection only or carcinoma *in situ* of the cervix). Patients with history of prostate cancer treated without radiotherapy and no evidence of disease are eligible.
4. Currently receiving any investigational agents.
5. A history of allergic reaction attributed to compounds of similar chemical or biologic composition to 5FU, oxaliplatin, or leucovorin.
6. Uncontrolled intercurrent illness including, but not limited to, ongoing or active infection, symptomatic congestive heart failure, unstable angina pectoris, cardiac arrhythmia, or psychiatric illness/social situations that would limit compliance with study requirements.
7. Pregnant and/or breastfeeding. Women of childbearing potential must have a negative serum pregnancy test within 14 days of study entry.
8. Known HIV-positivity and on combination antiretroviral therapy because of the potential for pharmacokinetic interactions with the study drugs. In addition, these patients are at increased risk of lethal infections when treated with marrow-suppressive

therapy. Appropriate studies will be undertaken in patients receiving combination antiretroviral therapy when indicated.

3.3 Inclusion of Women and Minorities

Both men and women and members of all races and ethnic groups are eligible for this trial.

4 Patient Registration

Patients must not start any protocol intervention prior to registration through the Siteman Cancer Center.

The following steps must be taken before registering patients to this study:

1. Confirmation of patient eligibility by Washington University
2. Registration of patient in the Siteman Cancer Center OnCore database
3. Assignment of unique patient number (UPN)

Once the patient has been entered in the Siteman Cancer Center OnCore database, the WUSM coordinator will forward verification of enrollment and the UPN via email.

4.1 Confirmation of Patient Eligibility

Confirm patient eligibility by collecting the information listed below and scanning and emailing it to the research coordinator listed in the *Siteman Cancer Center Clinical Trials Core Protocol Procedures for Secondary Sites* packet at least one business day prior to registering patient:

1. Your name and contact information (telephone number, fax number, and email address)
2. Your site PI's name, the registering MD's name, and your institution name
3. Patient's race, sex, and DOB
4. Three letters (or two letters and a dash) for the patient's initials
5. Currently approved protocol version date
6. Copy of signed consent form (patient name may be blacked out)
7. Planned date of enrollment
8. Completed eligibility checklist, signed and dated by a member of the study team
9. Copy of appropriate source documentation confirming patient eligibility

4.2 Patient Registration in the Siteman Cancer Center OnCore Database

Registrations may be submitted Monday through Friday between 8am and 5pm CT. Urgent late afternoon or early morning enrollments should be planned in advance and coordinated with the Washington University research coordinator. Registration will be confirmed by

the research coordinator or his/her delegate by email within one business day. Verification of eligibility and registration should be kept in the patient chart.

All patients at all sites must be registered through the Siteman Cancer Center OnCore database at Washington University.

4.3 Assignment of UPN

Each patient will be identified with a unique patient number (UPN) for this study. All data will be recorded with this identification number on the appropriate CRFs.

5 EVALUATION STUDIES

5.1 Pre-treatment

Within 12 weeks of day of simulation for RT but no later than the first radiation treatment:

- Staging study to evaluate extent of disease in the abdomen and pelvis: CT with IV contrast or MRI w/ IV contrast.
- Staging study to evaluate the lungs: CT scan of the chest
- CBC, CMP, CEA
- Pregnancy test (for women of childbearing potential) – within 14 days of first treatment
- Colonoscopy
- Examination by treating surgeon, medical oncologist, and radiation oncologist

If feasible it is strongly recommended that the following physical findings should be scored:

- Tumor location (distance in cm from the anal verge to the distal tumor margin)
- Circumferential lesion Y/N

- Imaging study to assess the local extent of the primary tumor, including T stage. A pelvic MRI is the preferred method for doing this; but depending on the lesion this could be endorectal ultrasound, or CT scan.
- FACT-C quality of life questionnaire

5.2 During Radiotherapy and Chemotherapy

Routine standard of care examinations and blood work will be done. This consists of a CMP and a CBC with differential prior to each cycle of chemotherapy and examination by the radiation oncologist during the week of radiation therapy and by a medical oncology physician or nurse with each cycle of chemotherapy. Please see Section 6 for radiation therapy guidelines and Section 7 for chemotherapy guidelines.

5.3 Completion of Chemotherapy/Post-Treatment Evaluation

Two to four weeks after completion of chemotherapy, patients will have the following assessments:

- FACT-C questionnaire.
- Surgical assessment w/ endoscopy (sigmoidoscopy preferred, rigid proctoscopy acceptable) to evaluate the extent of residual tumor
- MRI (when feasible) to evaluate ycT stage
- DRE (when feasible) to evaluate ycT stage

For patients with a cCR, non-operative management will be pursued. Patients will be assessed for sustained cCR by pelvic MR, endoscopy (sigmoidoscopy preferred, rigid proctoscopy accepted) and DRE every three months (not necessarily on the same day / appointment) for 1 year. Follow-up after 1 year will be left to the discretion of the treating physician, although DRE, pelvic MR and endoscopy every 3-4 months is recommended for the second year. CT chest/abdomen/pelvis every 6 months is recommended for at least the first 2 years. For patients with residual disease who do not meet criteria for cCR by 4 weeks after completion of the 8th cycle of FOLFOX, further therapy is mandated and at the discretion of the treating physicians. Patients whose disease is amenable to transanal endoscopic microexcision (TEM) or local excision (LE) may undergo TEM/LE to evaluate degree of residual disease. For those with pT1 disease without LVSI present, non-operative management may continue with evaluation noted above. For those with residual T2-3 disease or T1 with LVSI, extirpative surgery including TME is recommended with treatment at investigators discretion proceeding off-study.

Post-treatment lymph nodes are to be evaluated by imaging and reviewed in multidisciplinary tumor board with a radiologist and classified as progressive, persistent disease, indeterminate or benign. Patients with progressive or persistent lymph node disease will not be eligible for non-operative management and will undergo additional therapy. Patients with indeterminate or benign lymph nodes AND cCR of primary will undergo non-operative management.

5.4 Follow-up

The FACT-C questionnaire and follow-up visit will be done 10-14 months from treatment (radiotherapy) start date. Long-term follow-up will be done per routine policies of the treating physicians. It is recommended that there be follow up visits every 6 months with clinical exam until 5 years from study enrollment.

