6 RADIATION THERAPY GUIDELINES

6.1 Dose, Fractionation and Constraints

When feasible it is strongly recommended that radiotherapy begin on a Monday. It is accepted that occasional logistical delays may occur during radiotherapy treatment due to

machine downtime or other issues. Radiotherapy as administered during this study may take up to 10 business days without being considered a protocol deviation.

Radiotherapy will consist of five fractions, delivered once daily, to a total dose of 25 Gy at 5 Gy per fraction (PTV2500). Daily imaging to verify accurate setup is mandatory. It is required that at least 95% of the PTVs receive at least 95% of the prescription dose and that the maximum dose be $\leq 115\%$ of the prescription dose. Every effort should be made for 100% of the PTV to be covered by 95% of the prescription dose. The maximum allowed dose to small bowel is 25 Gy.

An optional concomitant boost may be delivered to the primary tumor of 1-2 Gy per day (30-35 Gy to tumor total). If a boost is given then the maximum allowed dose to small bowel is 25 Gy. Lymph nodes that are outside of the mesorectum may be boosted up to 35 Gy in 5 fractions also, as long as this small bowel constraint is met.

The following constraints are recommended when boosting lymph node or primary:

Bladder V20Gy < 15 cc. Dmax < 38 Gy.

Penile bulb V30Gy < 3 cc.

Femoral heads V30Gy < 10 cc.

Skin V36.5Gy < 10 cc. Dmax < 38.5 Gy.

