11 STUDY CALENDAR

	Screening ⁴	During Radiotherapy	Day 1 of Each Cycle of Chemotherapy ⁸	Completion of Chemotherapy ¹⁰	10 to 14 Months after Radiotherapy	Long-term Follow-up ⁹
Informed consent	X					
H&P	X	X (once)	X	X	X	
CBC diff, plts	X	X (once)	X			
CMP	X		X			
Pregnancy test ⁵	X ⁶					
Colonoscopy or barium enema or Hypaque enema	X ¹¹					
Surgical assessment with proctoscopy or sigmoidoscopy				X		
Digital rectal exam	X			X		
Staging study to evaluate disease in abdomen and pelvis ¹	X					
Staging study to evaluate disease in lungs ²	X					
Imaging study to assess local extent of primary tumor ³	X			X		
Radiotherapy		X ⁷				
FOLFOX / CAPEOX			X			
FACT-C	X			X	X	

AE assessment	AEs should be collected through 1 year following the start of RT	
---------------	--	--

1. CT with contrast or MRI or PET/CT or PET/MRI
2. Chest x-ray or CT of the chest or PET/CT
3. Pelvic MRI (preferred), endorectal ultrasound, MRI, CT scan
4. Within 8 weeks of day of simulation for RT but no later than the first radiation treatment
5. Women of childbearing potential only
6. No more than 14 days prior to the first day of treatment
7. 5 fractions delivered over the course of 5 days (preferably starting on a Monday). Optional concomitant boost may be delivered to the primary tumor of 1-2 Gy per day (30-35 Gy to tumor total). If a boost is given then the maximum allowed dose to small bowel is 25 Gy.
8. Chemotherapy should start 2 to 4 weeks after the end of RT. Each cycle is 14 days; a total of 8 cycles of chemotherapy will be given
9. Long-term follow-up will be done per routine policies of the treating physicians. It is recommended that there be follow up visits every 6 months with clinical exam until 5 years from study enrollment. Data will be collected from the medical record every 6 months on progression/recurrence and survival.
10. 3-8 weeks after the end of chemotherapy
11. Within 12 weeks of day of simulation for RT but no later than the first radiation treatment

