12 DATA SUBMISSION SCHEDULE

Case report forms with appropriate source documentation will be completed according to the schedule listed in this section.

Form	Completion Schedule
On-Study Form	Time of registration
Radiation Therapy Form	Completion of RT
Chemotherapy Form	At the end of each cycle of chemotherapy
RECIST Form	Baseline Completion of chemoradiation
Follow-Up Form	1 year after the start of RT
FACT-C	Baseline Completion of chemoradiation 10-14 months after chemoradiation
Long-Term Follow-Up Form	Every 6 months for 5 years after the start of RT
Adverse Events Form	Ongoing

Any queries generated by Washington University must be responded to within 28 days of receipt by the participating site. The Washington University research team will conduct a regular review of data status at all secondary sites, with appropriate corrective action to be requested as needed.

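### The one-year FACT-C has two time origins: start of radiotherapy in Section 5.4, but end of chemoradiation, about 4 to 6 months later, in Section 12

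*Combined protocol and SAP*

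**What the plan says.** Section 5.4 ties the late questionnaire and the follow-up visit together and counts from the first day of radiotherapy: "The FACT-C questionnaire and follow-up visit will be done 10-14 months from treatment (radiotherapy) start date".

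The Section 11 calendar heads the matching column "10 to 14 Months after Radiotherapy", without saying whether that means the start or the end of radiotherapy.

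Section 12, the schedule by which case report forms are completed, lists three FACT-C time points: "Baseline Completion of chemoradiation 10-14 months after chemoradiation". In the same table the Follow-Up Form is due "1 year after the start of RT".

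Section 5.3 places the middle FACT-C after chemotherapy: "Two to four weeks after completion of chemotherapy, patients will have the following assessments". The calendar likewise puts it in the completion-of-chemotherapy column.

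Secondary objective 4 (Sections 2.2 and 16.1) and the analysis in Section 16.5 use the late FACT-C to describe anorectal function at one year. Neither states from when the year is counted.

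**The concern.** The same 10-14 month window is attached to two different events. Treatment is sequential, with chemotherapy lasting 15 or 16 weeks and starting weeks after radiotherapy, so the two events are months apart. Section 12 also gives two origins to what Section 5.4 treats as a single visit: the Follow-Up Form counts from the start of radiotherapy and the FACT-C from the end of chemoradiation.

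At stake is the meaning of the one-year functional result. Staff who work from the form schedule would collect the questionnaire well after one year from radiotherapy start. That is also after grade 3 and higher adverse events stop being collected under Section 9.6 (one year from radiotherapy start), so reported function and toxicity would describe different periods. If practice differs between sites or staff, the summary would mix patients at quite different distances from their last chemotherapy. A questionnaire not collected at one year cannot be obtained afterwards.

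**Working it through.** **What the Section 12 row means by chemoradiation.** No FACT-C is scheduled at the end of radiotherapy. The only questionnaire between baseline and the late one is the post-chemotherapy one in Section 5.3. The row's completion-of-chemoradiation entry must be that one, so the next entry in the row counts from the end of chemotherapy.

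**Inputs**

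- Radiotherapy, shortest: "5 fractions delivered over the course of 5 days" (Section 11, footnote 7), so 4 days from first to last fraction.
- Radiotherapy, longest: "Radiotherapy as administered during this study may take up to 10 business days without being considered a protocol deviation" (Section 6.1), taken as 14 calendar days (an assumption).
- Gap from radiotherapy to chemotherapy: 2 to 4 weeks, so 14 to 28 days (Section 7.1).
- Chemotherapy: 8 FOLFOX courses or 5 capecitabine/oxaliplatin cycles (Section 7.1).
- Permitted total delay: up to 4 weeks, so 0 to 28 days (Section 7.1).
- One month = 30.44 days. The end of chemoradiation is taken as the end of the last cycle.

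**The plan's own durations.** FOLFOX: 8 × 14 = 112 days = 16 weeks. Capecitabine/oxaliplatin: 5 × 21 = 105 days = 15 weeks. Both agree with Section 7.1.

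**Offset between the two origins** = radiotherapy + gap + chemotherapy + delay. The last column adds 10 and 14 months to that offset.

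| Course | Sum (days) | Offset | Section 12 window, months from radiotherapy start |
|---|---|---|---|
| Capecitabine/oxaliplatin, fastest | 4 + 14 + 105 + 0 = 123 | 4.04 months | 14.04 to 18.04 |
| FOLFOX, fastest | 4 + 14 + 112 + 0 = 130 | 4.27 months | 14.27 to 18.27 |
| Capecitabine/oxaliplatin, slowest | 14 + 28 + 105 + 28 = 175 | 5.75 months | 15.75 to 19.75 |
| FOLFOX, slowest | 14 + 28 + 112 + 28 = 182 | 5.98 months | 15.98 to 19.98 |

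**Gap between the windows.** The Section 5.4 window closes at 14 months. The Section 12 window opens 14.04 − 14 = 0.04 month (about 1 day) later on the fastest course and 15.98 − 14 = 1.98 months (about 60 days) later on the slowest.

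**Sensitivity: counting to the last drug day, fastest courses**

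- Capecitabine/oxaliplatin: 4 + 14 + (4 × 21 + 13) = 115 days = 3.78 months. Overlap 14 − 13.78 = 0.22 month, about 7 days.
- FOLFOX: 4 + 14 + (7 × 14 + 2) = 118 days = 3.88 months. Overlap 0.12 month, about 4 days.

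**Time since the end of chemotherapy when the FACT-C is completed**

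- Under Section 5.4: from 10 − 5.98 = 4.02 months to 14 − 4.04 = 9.96 months.
- Under Section 12: 10 to 14 months.

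**Calendar against Section 5.4.** If the column header means the end of radiotherapy, it differs from Section 5.4 by 4 to 14 days (0.13 to 0.46 month), which is small within a four-month window.

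**The case against.** The protocol does not define chemoradiation and is loose with related terms. Secondary objective 3 speaks of toxicity after chemoradiotherapy, while Section 16.5 describes the same item as toxicity after radiotherapy. If the Section 12 row meant radiotherapy alone, the conflict would shrink to days. The mixed usage is real, but this reading does not fit the row, where completion of chemoradiation can only be the post-chemotherapy questionnaire.

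The day counts depend on convention. Counted as elapsed days, 10 business days span 11 to 13 days rather than 14, so the slowest course takes 179 to 181 days. Counting radiotherapy as 5 to 12 days gives an overall range of 124 to 180. The 1-day and 60-day endpoints are therefore approximate. About 4 to 6 months, with little or no overlap, holds under every convention tried.

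The practical harm is conditional. Section 5.4, the calendar and the Follow-Up Form all point to a visit timed from radiotherapy, so the FACT-C row is the outlier and staff may never act on it. Appendix A has a completion date on the form, so off-window questionnaires could be identified. Section 5.4 followed exactly still leaves a spread of 4 to 10 months since chemotherapy, which the correction does not remove. The output is descriptive, with no test or decision rule. All of this stands. It limits the severity but does not reconcile the two sections.

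**Conclusion.** The inconsistency is real and should be corrected. Two current sections time the same questionnaire from events about 4 to 6 months apart, and a questionnaire that is on time under one will almost always be out of window under the other. Following Section 12 would place the one-year measure at about 14 to 20 months from radiotherapy start.

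This rests on reading chemoradiation as the whole sequence of radiotherapy and chemotherapy, and on total delay staying within 4 weeks. Longer delays, which Section 7.1 refers to the Principal Investigator, would widen the difference. Confidence is high that the mismatch exists; whether it does harm depends on which section staff follow. Only a descriptive secondary endpoint in about 20 patients is affected.

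**What to change.** Use one time origin. Change the Section 12 FACT-C row and the Section 11 column header so that both count 10-14 months from the start of radiotherapy. That origin already governs Section 5.4, the Follow-Up Form and adverse event collection. A short clause in secondary objective 4 and Section 16.5 saying that the year runs from the start of radiotherapy would close the remaining gap, since neither now names an origin.

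The core correction is one table row and one column header, and the clause is optional wording. No visit, form or assessment is added.
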